1.3 Exploratory Objectives

- Compare the rates of epithelioid hemangioendothelioma progression prior to starting trametinib to rates on treatment by central review of radiology images
- Evaluate the effect of trametinib on change in tumor volume and compare to RECIST1.1 response through central imaging review
- Evaluate the effect of trametinib on markers of inflammation including c-reactive protein (CRP), erythrocyte sedimentation rate (ESR) and plasma connective tissue growth factor (CTGF).

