3. PATIENT SELECTION

3.1 Eligibility Criteria

- 3.1.1 Patients must have measurable disease, defined as at least one lesion that can be accurately measured in at least one dimension (longest diameter to be recorded for non-nodal lesions and short axis for nodal lesions) as ≥ 20 mm (≥ 2 cm) with conventional techniques or as ≥ 10 mm (≥ 1 cm) with spiral CT scan, MRI, or calipers by clinical exam. Baseline imaging must be obtained within 30 days of Day 1 of study. See Section 11 for the evaluation of measurable disease.
- 3.1.2 Patients must have histologically confirmed epithelioid hemangioendothelioma which is metastatic or locally advanced (unresectable), and tumor tissue (paraffin-embedded tissue block or tumor tissue on unstained glass slides) available for fusion FISH analysis at Cleveland Clinic. Patient tumor tissue stored in pathology archives may be used for fusion FISH; a new biopsy is not mandatory.

- 3.1.3 Patients must have evidence of disease progression per RECIST1.1 prior to enrollment or have evidence of cancer-related pain requiring symptom management with narcotic analgesics.
- 3.1.4 Because there is no established standard or approved drug therapy for treatment of EHE, patients previously untreated or treated with drug therapy for EHE are eligible. There is no limit on the number of prior regimens used to be eligible.
- 3.1.5 Age ≥ 15 years. EHE is very unlikely to arise before the age of 15 years.
- 3.1.6 ECOG performance status ≤ 2 (Karnofsky $\geq 60\%$, see Appendix A).
- 3.1.7 Life expectancy of greater than 6 months.
- 3.1.8 Able to swallow orally-administered medication and does not have any clinically significant gastrointestinal abnormalities that may alter absorption such as malabsorption syndrome or major resection of the stomach or small bowel.
- 3.1.9 All prior treatment-related toxicities must be CTCAE v5 grade ≤ 1 (**except alopecia**) at the time of enrollment.
- 3.1.10 Patients must have normal organ and marrow function as defined below within 2 weeks of patient registration (for blood results) and 30 days of registration for LVEF assessment:
 - Absolute neutrophil count (ANC) $\geq 1 \times 10^9/L$
 - Hemoglobin ≥ 9 g/dL, patients may receive transfusion to meet criterion
 - Platelets $\geq 75 \times 10^9/L$
 - Albumin ≥ 2.5 g/dL

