5.5 Duration of Therapy

In the absence of treatment delays due to adverse event(s), treatment may continue for 52 cycles or until one of the following criteria applies:

- Disease progression per RECIST,
- Clinical progression,
- Intercurrent illness that prevents further administration of treatment,

- Unacceptable adverse event(s),
- Patient decides to withdraw from the study
- Pregnancy
 - All women of child bearing potential should be instructed to contact the investigator immediately if they suspect they might be pregnant (e.g., missed or late menstrual period) at any time during study participation.
 - The investigator must immediately notify CTEP in the event of a confirmed pregnancy in a patient participating in the study.
- General or specific changes in the patient's condition render the patient unacceptable for further treatment in the judgment of the investigator.

Patients with clinical progression or disease progression per RECIST who are benefitting from trametinib in reduction of tumor-related symptoms may continue on treatment with trametinib after discussion with the Study PI and CTEP Medical Monitor and approval.

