9.4.1.2 Assessment

9.4.1.2.1. Sites of tumor will be imaged by CT or MRI using standard protocols.

9.4.1.2.2. Imaging tumor will occur within 30 days prior to starting drug, after cycles 2, 4 and 6 and thereafter approximately every 12 weeks. For patients with evidence of disease progression prior to enrollment, CT or MRI scans documenting progression will also be reviewed.

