13.4 Analysis of Exploratory Endpoints

Exploratory correlative studies will evaluate rates of EHE growth prior to starting trametinib to growth rates on treatment, the change in c-reactive protein (CRP), erythrocyte sedimentation rate (ESR), plasma connective tissue growth factor (CTGF) and tumor volume as potential biomarkers of EHE activity, and the effect of trametinib on MAP kinase activation.

Digital files of cross-sectional radiology images (CT and MRI) will be provided to [name] (Columbia University, NY) to evaluate the change in rate of EHE growth pre-trametinib therapy and on trametinib. Evidence of tumor progression per RECIST will be required for enrollment of patients (except in setting of severe tumor-related pain); therefore, longitudinal pre-treatment radiology images will be available in the majority of cases for comparison. A 50% or more reduction in the change in tumor size/unit of time following start of treatment with trametinib will be considered clinically significant. McNemar test will be used to compare the number of patients with EHE progression prior to starting trametinib to the number

of patients with EHE progression during treatment.

Patient CTGF samples collected at indicated time points will be run in triplicate and average values used for the comparison. The CTGF, CRP and ESR levels over time will be used as time-dependent variables in a Cox model to determine the association with EHE survival.

The agreement of change in tumor volume and in tumor size assessed by RECIST will be summarized with a scatterplot. The Pearson correlation coefficient (or Spearman, if more appropriate) will be assessed to determine the strength of the agreement. Agreement of the tumor classifications (response versus no response) will be summarized as the raw agreement and with a Kappa Statistic. The association of the change in tumor volume with survival will be evaluated in two ways. The first will be to use the change in tumor volume as a time dependent variable in a Cox model. The second will be a landmark analysis (done at either the first radiographic assessment or at the second radiographic assessment) to compare the survival of patients classified as a responder (based on tumor volume) to those who have not responded by the selected landmark time. Patients who died prior to the landmark time point will be omitted from analysis.

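### The exploratory McNemar test of progression before versus during trametinib does not measure a drug effect: the entry rule largely sets the before count, and neither period has a stated length

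*Combined protocol and SAP*

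**What the plan says.** The parent objective in section 1.3 is to "Compare the rates of epithelioid hemangioendothelioma progression prior to starting trametinib to rates on treatment by central review of radiology images". Section 13.4 gives two analyses for it. The first is a per-patient growth rate: "A 50% or more reduction in the change in tumor size/unit of time following start of treatment with trametinib" is to count as clinically significant. The second is a significance test on a yes/no outcome: "McNemar test will be used to compare the number of patients with EHE progression prior to starting trametinib to the number", the second count being those who progress while on the drug. No alpha, sidedness or exact/asymptotic form is given.

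The entry rule in section 3.1.3 reads: "Patients must have evidence of disease progression per RECIST1.1 prior to enrollment or have evidence of cancer-related pain", the pain being severe enough to need narcotic analgesics. Section 13.4 restates the rule in the same paragraph as the test: "Evidence of tumor progression per RECIST will be required for enrollment of patients (except in setting of severe tumor-related pain". Section 9.4.1.2 adds: "For patients with evidence of disease progression prior to enrollment, CT or MRI scans documenting progression will also be reviewed". Section 5.5 bounds the on-treatment period: "treatment may continue for 52 cycles or until one of the following criteria applies", the criteria including progression, adverse events and withdrawal.

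**The concern.** McNemar's null hypothesis is that the two marginal proportions are equal. That is a sensible null for a drug effect only if an untreated patient would be equally likely to be counted as progressed in each period. Here patients are mostly admitted because they had progressed, so the first proportion starts near its ceiling by design. The second depends on how long each patient is watched.

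The plan gives no look-back length, no landmark on treatment and no matching of the two. It also has no rule for a patient who stops for toxicity or withdraws before progressing. Such a patient could be counted as not having progressed during treatment, and so as evidence for the drug.

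In a single-arm trial of a disease that section 2.1 describes as sometimes stable for years, a small p-value from this test could be read as slowing by trametinib, and a large one as failure to slow. Either may mainly reflect the mix of entry routes and the time of reading.

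**Working it through.** The plan states no size or power for this test, so there is no figure of its own to reproduce.

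**Inputs**

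- n = 27, the fusion-positive target in section 13.2. Section 13.4 does not say which patients enter this test, so this is an assumption.
- k = number of the 27 counted as progressed before. The documents give no number, so k is varied from 18 to 27.
- q = probability of progression on treatment by the reading time with an inactive drug, taken as the same whatever the entry route. The documents give no untreated rate. Two values from section 2.1 are used, both from treated patients. Sorafenib: 38.4% progression-free at 6 months, so q = 1 - 0.384 = 0.616. Retrospective series: median PFS 4.8 months; with an exponential curve, q = 1 - 2^(-6/4.8) = 0.580.
- Two-sided exact McNemar test at an assumed 0.05.

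**Rejection rule**

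Let b be patients progressed before only and c those progressed during only. For b > c,

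p = 2 × Σ(i=0..c) C(b+c, i) / 2^(b+c).

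If all 27 entered on progression, c must be 0, and b = 6 gives p = 2/2^6 = 0.031. Any six patients without recorded progression on treatment, for whatever reason, give significance. With c = 1, 2 or 3, b must be at least 8, 10 or 12.

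**Chance of a false reduction**

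With b ~ Binomial(k, 1-q) and c ~ Binomial(27-k, q), the probability is summed over all (b, c) with b > c and p < 0.05.

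| Entered on progression | q = 0.616 | q = 0.580 |
|---|---|---|
| 27/27 | 97.7% | 99.1% |
| 24/27 | 49.5% | 64% |
| 22/27 | 16.3% | 27% |
| 20/27 | 3.3% | 7% |
| 18/27 | 0.4% | 1% |

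**Effect of the reading time** (exponential curve, no-effect median 4.8 months)

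| Read at | q | False reduction, 27/27 | False reduction, 22/27 |
|---|---|---|---|
| 4 months | 0.439 | about 100% | 80% |
| 6 months | 0.580 | 99% | 27% |
| 12 months | 0.823 | 34% | 0.03% |
| 24 months | 0.969 | 0.02% | about 0% |

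At 24 months the error reverses: a false increase has probability 52% at 20/27 and 88% at 18/27.

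**Active and inactive drugs give the same result.** An inactive drug (median 4.8 months) read at 12 months gives 1 - 2^(-12/4.8) = 82.3% progressed. A drug that doubles the median to 9.6 months, read at 24 months, gives 1 - 2^(-24/9.6) = 82.3%. Both give a 34% chance of a significant reduction at 27/27.

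**Control.** With no selection on progression and equal periods, the exact test on 27 pairs has two-sided size 2.4-2.6% for progression probabilities from 0.3 to 0.693. The fault is the selection and the unmatched periods, not the test or the small sample.

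**Would a test of slopes do better?** A simulation with no drug effect, and entry on a measured increase of at least 20%, was run over a grid of assumptions that the documents do not give: scans 4 months apart before and 4 or 6 months on treatment; mean log growth 0.02-0.04 per month; between- and within-patient SD 0.01-0.03 each; measurement SD 0.05-0.10; 600 trials per setting. A Wilcoxon test of on-treatment against pre-treatment slope found false slowing in 60-100% of trials, against 2-3% without selection. Between 18% and 80% of patients met the 50% reduction with no drug effect.

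**The case against.** **It is exploratory.** No decision rule is attached, and the ORR conclusion is untouched. This stands and limits the consequence. It does not make the p-value interpretable.

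**The time-based growth measure is already planned.** True, and that makes the fix cheap. The McNemar test still sits beside it as the test of progression before against during.

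**The headline figure is an extreme.** The 98-99% needs every patient to have entered on progression and a 6-month reading that no section sets. With 20 of 27 it is 3-7%, and at 24 months it is about 0% even at 27/27. This is correct, and it supports the point: the answer is governed by entry mix and reading time.

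**The 24-month figures lean on an exponential tail.** Section 2.1 shows progression slowing on sorafenib, from 38.4% to 30.7% progression-free between months 6 and 9. That is a hazard of ln(38.4/30.7)/3 = 0.075 per month, against ln 2/4.8 = 0.144 assumed. Carrying it forward gives 1 - 0.307 × exp(-0.075 × 15) = 90% progressed at 24 months, and the false increase falls to about 10% at 20/27 and 38% at 18/27. At 22/27 or more it cannot occur, because at most five patients can be discordant in that direction. The sizes change; the direction of error remains possible.

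**The null rates come from treated patients, and n could differ.** Both are fair. With 20 evaluable pairs and q = 0.616, the false reduction is 84% at 20/20 and 6% at 16/20: again driven by the mix.

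**The periods are partly defined.** Section 5.5 bounds treatment, scans are scheduled and RECIST defines progression. What is missing is a stated and matched length. Central review may also fail to confirm some local progressions, so the entry rule sets the before count largely, not wholly.

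**McNemar could be kept with fixed windows.** That removes the dependence on reading time but not the selection: at a fixed 6 months the false-reduction rate at 27/27 is still 98-99%.

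**The replacement proportion is itself biased.** It is, as the 18-80% shows. Hence it should be descriptive only, with the bias stated.

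**Conclusion.** The concern holds. As written, the McNemar test compares a proportion largely fixed by eligibility with one that depends on an unspecified length of observation, so neither a significant nor a non-significant result speaks to a drug effect. For an inactive drug read at 6 months, the chance of a false reduction runs from about 1% or less (18 of 27 entering on progression) to 98-99% (27 of 27). At late readings with many pain entrants, a false increase is possible. These sizes rest on an assumed n of 27, an assumed entry mix, progression rates borrowed from treated patients and, for the readings by month, an exponential curve. The conclusion does not depend on any one of them. The analysis is exploratory and the primary ORR decision is unaffected, so this should be corrected before analysis but does not threaten the trial's main result.

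**What to change.** In section 13.4, delete the McNemar test and its p-value. In its place:

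- Report descriptively, by central review, each patient's change in tumour size per unit time before and on treatment, where pre-treatment scans exist.
- Report the proportion meeting the protocol's own threshold of at least a 50% reduction, with an exact 95% confidence interval, separately for patients who entered on progression and those who entered for pain.
- State which scans and what time window each rate uses.
- State that pre-treatment growth is selected on progression, so some slowing is expected from regression to the mean without any drug effect.
- Do not substitute a Wilcoxon or other significance test of pre-treatment against on-treatment slope; it carries the same selection bias.

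The cost is a wording change and the loss of a p-value for this comparison. Patients with a single pre-treatment scan drop out of it. Section 9.4.1.2 provides for baseline scans and those documenting progression, but does not clearly require older scans or any prior scans for pain entrants, so that subgroup may be small or empty. No new visits or imaging are needed.

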2.4.4 Tumor volume

We hypothesize that a change in volume of EHE will correlate with EHE response to treatment. Analysis of change in tumor volume identified more patients than RECIST 1.1 with response and correlated with survival in a retrospective analysis of Ewing sarcoma treated with anti-insulin-like growth factor therapy (Koshkin et al., 2016). [name] has experience in determining tumor volume using Columbia University's semi-automated solid tumor segmentation software (Koshkin et al., 2016). Digital radiology files will be obtained from treating centers and sent to [name] for analysis. Tumor volume will be determined for up to 3 dominant lesions per patient and change in volume over time will be calculated. Tumor response by volume will be compared to response by RECIST 1.1 and correlated with survival. Based on prior studies, increase in tumor volume of 100% or more will be scored as progression and decrease in volume of 45% or more will be scored as response (Koshkin et al., 2016).

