9.4 Special Studies

9.4.1 Tumor Volume

9.4.1.1 Measure: Change in volume of EHE on treatment with trametinib. In a retrospective analysis, a change in tumor volume identified more patients than RECIST 1.1 with response and correlated with survival in a prospective trial of Ewing sarcoma treated with anti-insulin-like growth factor. We will assess changes in tumor volume over time, compare this to response by RECIST 1.1 criteria and correlate with survival. An increase in tumor volume of 100% or more will be scored as progression and decrease in volume of 45% or more will be scored as response.

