Target lesions. All measurable lesions up to a maximum of 2 lesions per organ and 5 lesions in total, representative of all involved organs, should be identified as **target lesions** and recorded and measured at baseline. Target lesions should be selected on the basis of their size (lesions with the longest diameter), be representative of all involved organs, but in addition should be those that lend themselves to reproducible repeated measurements. It may be the case that, on occasion, the largest lesion does not lend itself to reproducible measurement in which circumstance the next largest lesion which can be measured reproducibly should be selected. A sum of the diameters (longest for non-nodal lesions, short axis for nodal lesions) for all target lesions will be calculated and reported as the baseline sum diameters. If lymph nodes are to be included in the sum, then only the short axis is added into the sum. The baseline sum diameters will be used as reference to further characterize any objective tumor regression in the measurable dimension of the disease.

Non-target lesions. All other lesions (or sites of disease) including any measurable lesions over and above the 5 target lesions should be identified as **non-target lesions** and should also be recorded at baseline. Measurements of these lesions are not required, but the presence, absence, or in rare cases unequivocal progression of each should be noted throughout follow-up.

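### Section 13.4 uses a correlation as the measure of agreement between volume change and RECIST change, and the planned kappa covers response only, not progression or size of change

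*Combined protocol and SAP*

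**What the plan says.** Section 13.4 plans three things for this comparison.

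- A plot: "The agreement of change in tumor volume and in tumor size assessed by RECIST will be summarized with a scatterplot".
- A coefficient: Pearson's, or Spearman's if that suits the data better, "will be assessed to determine the strength of the agreement".
- A categorical comparison: "Agreement of the tumor classifications (response versus no response) will be summarized as the raw agreement and with a Kappa Statistic".

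The volume cut-offs are in Section 9.4.1: "An increase in tumor volume of 100% or more will be scored as progression", and a "decrease in volume of 45% or more will be scored as response". The RECIST cut-offs in Section 11.1.4.1 are a 30% fall in the sum of diameters for partial response, and a 20% rise with at least 5 mm absolute increase for progression.

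The lesion rules differ. Section 2.4.4 has "Tumor volume will be determined for up to 3 dominant lesions per patient"; Section 11.1.2 has "All measurable lesions up to a maximum of 2 lesions per organ and 5 lesions in total".

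Section 13.4 does not plan a conversion to a common scale, an estimate of bias, limits of agreement or a concordance coefficient, and it does not compare progression calls. Section 1.3 lists the comparison as an exploratory objective.

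**The concern.** The question posed is agreement, but the statistic named answers a different one. Pearson's r is unchanged if one measure is shifted by a constant or multiplied by a positive factor, and Spearman's depends only on ranks. If volumetry understated every patient's change by the same proportion, or lay a fixed number of points below RECIST throughout, either coefficient could still be close to 1.

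This matters because Sections 2.4.4 and 9.4.1 motivate the volume measure by a retrospective analysis in another sarcoma in which volume found more responders than RECIST 1.1. That is a statement about systematic difference, the feature that a correlation leaves out. The exploratory report could describe as strong agreement a relationship that is only strong association.

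**Working it through.** The plan states no sample size, expected value or threshold for this comparison, so there is no figure to reproduce. The illustrations use 27 patients, the number of fusion-positive patients targeted in Section 13.1. The distributions of change, the spherical lesions and the biases are assumptions; the documents give none. Baseline is taken as the smallest sum, the 5 mm condition is taken as met, and new and non-target lesions are ignored.

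**Cut-offs on one scale.** For a sphere, volume change v and diameter change d satisfy v = (1 + d)^3 - 1, so d = (1 + v)^(1/3) - 1.

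| Call | RECIST cut-off | Same, as volume | Volume cut-off | Same, as diameter |
|---|---|---|---|---|
| Response | -30% | 0.70^3 - 1 = -65.7% | -45% | 0.55^(1/3) - 1 = -18.1% |
| Progression | +20% | 1.20^3 - 1 = +72.8% | +100% | 2^(1/3) - 1 = +26.0% |

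Volume response is therefore the easier call and volume progression the harder one, even with perfect measurement.

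**Illustration 1: proportional bias.** Let RECIST change d have mean -10% and SD 20%. Let equivalent-diameter change from volume be e = 0.5d + noise, noise SD 3 points.

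- cov(d, e) = 0.5 × 0.20² = 0.0200; var(d) = 0.0400; var(e) = 0.25 × 0.0400 + 0.03² = 0.0109.
- r = 0.0200 / √(0.0400 × 0.0109) = 0.958.
- Means are -0.10 and -0.05, squared difference 0.0025. Lin's concordance = 2 × 0.0200 / (0.0400 + 0.0109 + 0.0025) = 0.749.
- Under the protocol's cut-offs, simulation gives raw response agreement of about 93% and kappa of about 0.71.

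**Illustration 2: perfect spheres, response.** Take 27 diameter changes evenly spaced from -29% to +10% (step 1.5 points). Pearson r between d and v is 0.994 and Spearman is 1. No patient reaches -30%. Eight reach -18.1% (from -29% to -18.5%). Raw agreement is 19/27 = 70% and kappa is 0.

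**Illustration 3: perfect spheres, progression.** Take 27 diameter changes evenly spaced from -10% to +25%. Here r = 0.996. There are no responders by either method, so response agreement is 100% and kappa is undefined. RECIST calls 4 progressions; volume calls none. The planned table does not show this.

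**Illustration 4: size of change.** Take 27 diameter changes evenly spaced from -15% to +19%, with volume showing 40% of each (e = 0.4d). Here r = 0.999, and neither method calls any response or progression. The two differ by up to 0.6 × 19 = 11.4 points, and concordance on the diameter scale is 0.68. No classification table would show this; a concordance coefficient or limits of agreement would.

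**Precision of the remedy at n = 27.** With t(0.975, 26 df) = 2.06 and SD that of the paired differences, the 95% half-width is 2.06/√27 = 0.40 SD for the mean difference. For each Bland-Altman limit it is 2.06 × √(1/27 + 1.96²/52) = 0.68 SD. These are wide but reportable.

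**The case against.** The strongest reply is that the correlation does not stand alone. Section 13.4 also plans a scatterplot, raw agreement and kappa. A reader might infer that the plan would report strong agreement whether or not the two measures give the same answer, or that kappa is no help because its two cut-offs differ. The documents do not support either. Differing cut-offs are what produce discordant calls, and kappa counts them. It is 0 in illustration 2. With spherical lesions and normally distributed change (mean -10%, SD 15% to 25%), simulation gives r of 0.94 to 0.97 but kappa of only about 0.39 to 0.62, so the planned kappa would warn the reader. In illustration 1, kappa of 0.71 is close to the concordance of 0.75. This reply stands for response calls. It does not reach progression or size of change, and a low kappa cannot say whether the measurements or the cut-offs disagree.

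Two more inferences are tempting. One is that the differing lesion sets inflate r. They would tend to lower it, and they are permitted rather than certain, since a patient with few lesions may have the same set under both rules. The other is that raw percent volume and percent diameter differ by many points (22 to 34 on average in the simulation just described), which looks like disagreement. That gap reflects units only: for perfect spheres the two carry identical information. For quantities in different units a correlation is a reasonable description, so the fault lies in treating it as agreement.

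It can also be said that a RECIST sum restricted to the volume lesions is not RECIST 1.1 as Section 11.1.2 defines it. It might also need new diameters, because measurement of non-target lesions is not required. Both points are right, and they limit what the fix should ask for.

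**Conclusion.** The point holds in a limited form. Section 13.4 treats a correlation as the strength of agreement, and a correlation cannot detect constant or proportional bias: r = 0.96 can coexist with concordance of 0.75, and r = 0.99 with 0 versus 8 responders of 27. Raw agreement and kappa cover part of the gap. What remains uncovered is progression (4 RECIST versus 0 volume progressions of 27 in illustration 3), the size of change, and the separation of measurement disagreement from cut-offs that sit at -18% and -30% on a common diameter scale.

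These figures show what is possible, not what is expected; nothing in the documents suggests that volumetry is biased in this trial. The consequence is small. The comparison is exploratory, the primary response rate uses the local site's assessment (Section 13.1), and treatment continuation follows the treating investigator or site (Section 11.1.7). This is a minor improvement to a stated objective.

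**What to change.** In Section 13.4:

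1. Describe the Pearson or Spearman coefficient as a measure of association, and keep it with the scatterplot.
2. As the agreement measure, express volume change as equivalent-diameter change, (V/V0)^(1/3) - 1. Against change in the RECIST 1.1 sum as defined in Section 11.1.2, report the mean difference, Bland-Altman limits and Lin's concordance, with confidence intervals.
3. Add a matched-lesion comparison only as a sensitivity analysis, in patients whose diameters for the volume lesions already exist.
4. Extend the raw agreement and kappa table to include progression, using the cut-offs already in Section 9.4.1, and state that kappa will be reported as not estimable when neither method assigns more than one category.

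The cost is a short text edit and a few lines of code, with no new scans; under item 3 no new measurements either. The drawback is that the conversion assumes roughly isotropic change, and for summed volumes roughly proportional change across lesions. The plan should say so, because anisotropic change is one way in which volume may carry information that diameters do not.

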11.1.4 Response Criteria

11.1.4.1 Evaluation of Target Lesions

Complete Response (CR): Disappearance of all target lesions. Any pathological lymph nodes (whether target or non-target) must have reduction in short axis to <10 mm (<1 cm).

Partial Response (PR): At least a 30% decrease in the sum of the diameters of target lesions, taking as reference the baseline sum diameters.

Progressive Disease (PD): At least a 20% increase in the sum of the diameters of target lesions, taking as reference the smallest sum on study (this includes the baseline sum if that is the smallest on study). In addition to the relative increase of 20%, the sum must also demonstrate an absolute increase of at least 5 mm (0.5 cm). (Note: the appearance of one or more new lesions is also considered progressions).

Stable Disease (SD): Neither sufficient shrinkage to qualify for PR nor sufficient increase to qualify for PD, taking as reference the smallest sum diameters while on study.

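### The −45% volume response cut-off is looser than RECIST's −30% in diameters (about −18% in diameter if shrinkage is uniform), so the response kappa in 13.4 mixes cut-off stringency with disagreement between the measures

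*Combined protocol and SAP*

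**What the plan says.** Section 1.3 lists a comparison of tumor volume change with RECIST 1.1 response among the exploratory objectives.

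- **Volume criterion.** Section 9.4.1 (and 2.4.4) states: "decrease in volume of 45% or more will be scored as response". Section 2.4.4 takes the cut-offs from prior work and limits the measurement: "Tumor volume will be determined for up to 3 dominant lesions per patient".
- **RECIST criterion.** Section 11.1.4.1 defines partial response as "At least a 30% decrease in the sum of the diameters of target lesions", relative to baseline. Section 11.1.2 allows up to 5 target lesions, and 11.1.4.3 requires confirmation.
- **Categorical comparison.** Section 13.4: "Agreement of the tumor classifications (response versus no response) will be summarized as the raw agreement and with a Kappa Statistic".
- **Comparison without a cut-off.** Also in 13.4: "The agreement of change in tumor volume and in tumor size assessed by RECIST will be summarized with a scatterplot", with a Pearson or Spearman correlation.
- **Motivation.** Section 2.4.4 reports from a retrospective Ewing sarcoma analysis: "Analysis of change in tumor volume identified more patients than RECIST 1.1 with response".

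The plan does not say that the two response cut-offs differ in stringency, does not include an agreement analysis at equivalent cut-offs, and does not say how kappa will be interpreted.

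**The concern.** Volume changes roughly as the cube of diameter, so a 45% fall in volume and a 30% fall in diameter are not the same amount of shrinkage. If the volume criterion is easier to meet, two methods that rank and measure every patient identically will still classify some patients differently. Kappa then has a ceiling below 1 that depends on how many patients lie between the two cut-offs, and the reader cannot tell how much of any shortfall is cut-off and how much is measurement.

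The direction matters too. Because 2.4.4 motivates the analysis by a study in which volume found more responders, a similar excess here could easily be taken as support for volume as a more sensitive measure, when the looser threshold alone could produce it.

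**Working it through.** The plan gives no expected kappa, diameter equivalent or sample size for this comparison, so there is no stated figure to reproduce.

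**1. Converting the cut-offs.** Inputs: −45% volume (9.4.1) and −30% in sum of diameters (11.1.4.1). Assumption: every lesion shrinks by the same fraction in all three axes, so volume ratio = (diameter ratio)³.

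- −45% volume: 1 − 0.55^(1/3) = 0.181, a diameter decrease of 18.1%.
- −30% diameter: 1 − 0.70³ = 1 − 0.343 = 0.657, a volume decrease of 65.7%.

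Every target-lesion partial response is then also a volume response. The discordant patients are exactly those with diameter decreases from 18.1% up to, but not including, 30%.

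**2. Kappa when the measures agree perfectly.** Let r be the RECIST response rate, v the volume response rate and b = v − r the share of patients in the band. Since RECIST responders are nested in volume responders:

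- observed agreement po = 1 − b
- chance agreement pe = rv + (1 − r)(1 − v)
- kappa = (po − pe)/(1 − pe)

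Example with r = 0.20 and b = 0.10: v = 0.30, po = 0.90, pe = 0.06 + 0.56 = 0.62, kappa = 0.28/0.38 = 0.74.

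Using the 5% and 20% response rates of 13.1 for r, with b assumed:

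| RECIST rate | b = 5% | b = 10% | b = 20% |
|---|---|---|---|
| 20% | 0.86 | 0.74 | 0.55 |
| 5% | 0.64 | 0.46 | 0.27 |

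If b = 0, kappa is 1.

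**3. Illustrative size.** Assume best diameter change is normal and measurement is error-free. Then r = P(change ≤ −30%), v = P(change ≤ −18.1%), and extra volume responders = 27 × (v − r). The 27 is the fusion-positive target in 13.1 and 13.2, used only for scale.

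| Mean, SD (points) | RECIST | Volume | Kappa | Extra of 27 |
|---|---|---|---|---|
| −15, 15 | 15.9% | 41.9% | 0.415 | 7.0 |
| −15, 20 | 22.7% | 43.9% | 0.545 | 5.7 |
| −10, 15 | 9.1% | 29.5% | 0.386 | 5.5 |
| −10, 20 | 15.9% | 34.3% | 0.530 | 5.0 |
| −5, 15 | 4.8% | 19.2% | 0.349 | 3.9 |
| −5, 20 | 10.6% | 25.7% | 0.510 | 4.1 |
| 0, 15 | 2.3% | 11.4% | 0.306 | 2.5 |
| 0, 20 | 6.7% | 18.3% | 0.484 | 3.1 |

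Across this grid kappa is 0.31 to 0.55, with 2.5 to 7.0 extra volume responders. At the matched −65.7% cut-off the same perfectly concordant data give raw agreement and kappa of 1.00.

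**4. Relaxing uniform shrinkage.** Simulation of 400,000 patients. The common log size change has SD 0.22, each axis adds independent log variation with SD 0.1 or 0.2, the diameter is one of the three axes, and the RECIST rate is calibrated to 20% or 5% (all assumed).

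| RECIST rate | Axis SD | Volume rate at −45% | Kappa | Volume rate at −65.7% | Kappa |
|---|---|---|---|---|---|
| 20% | 0.1 | 42.0% | 0.51 | 18.5% | 0.76 |
| 20% | 0.2 | 35.5% | 0.51 | 15.7% | 0.58 |
| 5% | 0.1 | 14.5% | 0.46 | 4.0% | 0.69 |
| 5% | 0.2 | 9.1% | 0.49 | 2.5% | 0.44 |

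The excess of volume responders at −45% persists in all four cases and is gone at −65.7%. Kappa stays below 1 at the matched cut-off, and in the last case is no better than at −45%.

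**The case against.** **The criteria are meant to differ.** The volume cut-off is pre-specified from prior work, and a volume criterion may reasonably be tied to outcome rather than to RECIST geometry. Comparing two complete criteria as defined is a legitimate aim. This stands, and is why the −45% category and its kappa should stay.

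**The plan does not rest on kappa alone.** Section 13.4 also has the scatterplot and correlation, which use no cut-off, and Cox and landmark analyses of volume against survival. This stands, but none of these shows how much of the categorical disagreement comes from the cut-offs.

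**The 18% figure needs uniform shrinkage.** The documents do not assert it. If one axis is fixed and the other two shrink equally, −45% volume is 1 − 0.55^(1/2) = 25.8% in those axes, much nearer to 30%. This limits the size of the effect; in the non-uniform cases simulated, the excess was still present.

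**Stronger readings that a reader might infer.**

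- That a low kappa and an excess of volume responders are guaranteed. They are not: both depend on how many patients fall in the band. With 5% in it at a 20% RECIST rate, kappa is 0.86.
- That the planned kappa measures only the gap between cut-offs. It does not: volume uses up to 3 lesions against up to 5; confirmation is stated only for RECIST; new and non-target lesions enter the RECIST classification but not the stated volume rule; and shrinkage need not be uniform.
- That the progression cut-offs bias a kappa in the opposite direction. Under uniform growth, "An increase in tumor volume of 100% or more will be scored as progression" equals +26.0% in diameter (2^(1/3) − 1), and "At least a 20% increase in the sum of the diameters of target lesions" equals +72.8% in volume (1.2³ − 1), so volume is the stricter rule there. But 13.4 plans agreement only on response versus no response, so no progression kappa is affected.
- That the plan intends to read a low kappa as greater sensitivity of volume. The documents do not say so; the risk is one of interpretation.

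**Conclusion.** The point holds in a limited form. The two response cut-offs differ in stringency, and the plan neither says so nor separates that difference from disagreement between the measures. The conversions in step 1 are exact under uniform three-axis shrinkage and approximate otherwise. The kappa and extra-responder ranges in step 3 rest on assumed distributions and perfect measurement; they show that the effect can be material, and do not predict this trial's result.

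An excess of volume responders at −45% therefore cannot by itself show that volume is the more sensitive measure. Nor would disagreement remaining at matched cut-offs show a difference due to the method, because the lesion-count, confirmation and new- or non-target-lesion rules and the shape of shrinkage also contribute.

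The consequence is small: the comparison is exploratory, and the primary endpoint and treatment decisions use local RECIST assessment (13.1, 11.1.7). This is an optional improvement.

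**What to change.** In 13.4, keep the pre-set −45% response category with its raw agreement and kappa, and add wording such as:

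> As a sensitivity analysis, raw agreement, kappa and both discordant cell counts will also be reported with volume response defined as a decrease of at least 65.7%, the geometric equivalent of a 30% diameter decrease under uniform shrinkage. An excess of volume responders at −45% will not be interpreted as greater sensitivity of volume unless it persists at this cut-off. Disagreement remaining at this cut-off will be described as not explained by the cut-offs under uniform shrinkage, and not attributed to the measurement method alone.

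List beside the table the other differences between the criteria: number of lesions, confirmation, new and non-target lesions, and non-uniform shrinkage. No progression kappa is needed.

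The cost is a short addition to 13.4 and one table from data already being collected, with no new scans and no change to patient care. Fixing the second cut-off before the volume results are examined avoids a post hoc choice.
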